8.5 Withdrawal of individual subjects

Subjects can leave the study at any time for any reason if they wish to do so without any consequences. The investigator can decide to withdraw a subject from the study for urgent medical reasons.

8.5.1 Specific criteria for withdrawal (if applicable)

Not applicable

8.6 Replacement of individual subjects after withdrawal

If a participant decides to withdraw before start of treatment with Cabometyx, another patient will be recruited to replace this participant. If a participant withdraws after start of treatment, this patient will be regarded as 'lost to follow-up' and won't be replaced.

8.7 Follow-up of subjects withdrawn from treatment

All participants who received at least one dose of Cabometyx, will have study related follow-up for 3 years after the start of the study in order to establish PFS en OS. If a participant withdraws before start of Cabometyx, there will be no study related follow-up. Once study related follow-up is finished, patients will get follow-up as standard medical care.

8.8 Premature termination of the study

The Simon 2-stage design of this study prevents unnecessary exposure of an ineffective treatment. After the first stage (9 patients in each cohort) an interim analysis will be done to see whether continuation of the trial is indicated. See the sample size calculation for more details.

9. SAFETY REPORTING

9.1 Temporary halt for reasons of subject safety

In accordance to section 10, subsection 4, of the WMO, the sponsor will suspend the study if there is sufficient ground that continuation of the study will jeopardise subject health or safety. The sponsor will notify the accredited METC without undue delay of a temporary halt including the reason for such an action. The study will be suspended pending a further positive decision by the accredited METC. The investigator will take care that all subjects are kept informed.

9.2 AEs, SAEs and SUSARs

9.2.1 Adverse events (AEs)

Adverse events are defined as any undesirable experience occurring to a subject during the study, whether or not considered related to the investigational product. All adverse events reported spontaneously by the subject or observed by the investigator or his staff will be recorded.

9.2.2 Serious adverse events (SAEs)

A serious adverse event is any untoward medical occurrence or effect that

- results in death;
- is life threatening (at the time of the event);
- requires hospitalisation or prolongation of existing inpatients' hospitalisation;
- results in persistent or significant disability or incapacity;
- is a congenital anomaly or birth defect; or
- any other important medical event that did not result in any of the outcomes listed above due to medical or surgical intervention but could have been based upon appropriate judgement by the investigator.

An elective hospital admission will not be considered as a serious adverse event.

The investigator will report all SAEs to the sponsor without undue delay after obtaining knowledge of the events.

The sponsor will report the SAEs through the web portal *ToetsingOnline* to the accredited METC that approved the protocol, within 7 days of first knowledge for SAEs that result in death or are life threatening followed by a period of maximum of 8 days to complete the initial preliminary report. All other SAEs will be reported within a period of maximum 15 days after the sponsor has first knowledge of the serious adverse events.

9.2.3 Suspected unexpected serious adverse reactions (SUSARs)

Adverse reactions are all untoward and unintended responses to an investigational product related to any dose administered.

Unexpected adverse reactions are SUSARs if the following three conditions are met:

1. the event must be serious (see chapter 9.2.2);

2. there must be a certain degree of probability that the event is a harmful and an undesirable reaction to the medicinal product under investigation, regardless of the administered dose;
3. the adverse reaction must be unexpected, that is to say, the nature and severity of the adverse reaction are not in agreement with the product information as recorded in the Investigator's Brochure.

The sponsor will report expedited the following SUSARs through the web portal *ToetsingOnline* to the METC:

- SUSARs that have arisen in the clinical trial that was assessed by the METC;
- SUSARs that have arisen in other clinical trials of the same sponsor and with the same medicinal product, and that could have consequences for the safety of the subjects involved in the clinical trial that was assessed by the METC.

The remaining SUSARs are recorded in an overview list (line-listing) that will be submitted once every half year to the METC. This line-listing provides an overview of all SUSARs from the study medicine, accompanied by a brief report highlighting the main points of concern.

The expedited reporting of SUSARs through the web portal Eudravigilance or *ToetsingOnline* is sufficient as notification to the competent authority.

The sponsor will report expedited all SUSARs to the competent authorities in other Member States, according to the requirements of the Member States.

The expedited reporting will occur not later than 15 days after the sponsor has first knowledge of the adverse reactions. For fatal or life threatening cases the term will be maximal 7 days for a preliminary report with another 8 days for completion of the report.

9.3 Annual safety report

In addition to the expedited reporting of SUSARs, the sponsor will submit, once a year throughout the clinical trial, a safety report to the accredited METC, competent authority, and competent authorities of the concerned Member States.

This safety report consists of:

- A list of all suspected (unexpected or expected) serious adverse reactions, along with an aggregated summary table of all reported serious adverse reactions, ordered by organ system, per study;
- A report concerning the safety of the subjects, consisting of a complete safety analysis and an evaluation of the balance between the efficacy and the harmfulness of the medicine under investigation.

9.4 Follow-up of adverse events

All AEs will be followed until they have abated, or until a stable situation has been reached. Depending on the event, follow up may require additional tests or medical procedures as indicated, and/or referral to the general physician or a medical specialist. SAEs need to be reported till end of study within the Netherlands, as defined in the protocol

Monitoring Cabometyx is registered in advanced renal cell carcinoma. Additional toxicity is not expected in SGC. Therefore a DSMB deemed unnecessary. The study will be monitored according to the NFU guideline 'Kwaliteitsborging mensgebonden onderzoek 2.0'. For this study with a moderate risk, moderate intensive monitoring will be applied (see page 18 of the NFU guideline).

10. STATISTICAL ANALYSIS

10.1 Primary study parameter(s)

Following Simon's design (as described in section 4.4) for RECIST v1.1, the null hypothesis will be rejected if more than 2 responses out of 17 patients are observed; in that case the conclusion is that the drug should be further investigated. This design yields a type I error rate of 0.047 and power 0.81 when the true response rate is 0.25. A 95% CI for the overall response rate per RECIST v1.1 will be calculated using the binomial distribution. Next to this, responses (CR, PR, SD and PD) will be described using simple descriptive statistics.

10.2 Secondary study parameter(s)

- Assess the PFS
 - PFS will be estimated by a Kaplan-Meier curve
 - In SDC patients, PFS will be compared to PFS in AR-positive SDC patients which received ADT^{17,18} and HER2-positive SDC patients which received docetaxel plus trastuzumab.¹⁹
 - In ACC patients, PFS will be compared to PFS in ACC patients which received mitoxantrone monotherapy,^{20,21} vinorelbine monotherapy,²² epirubicin monotherapy,²³ or cisplatin plus anthracycline combination therapies²⁴
 - In other SGC patients, PFS will be described per individual case.
- Assess the OS
 - OS will be estimated by a Kaplan-Meier curve
 - In SDC patients, OS will be compared to a historical cohort of patients receiving best supportive care and a cohort receiving ADT.¹⁸
 - In ACC patients, median OS after disease recurrence is 6.4 years, and median OS after metastasis is 3.7 years.²⁵ OS of our study patients will be compared to these data and to OS data of phase II studies in ACC mentioned above (assess the PFS).
 - In other SGC patients, survival will be described per individual case
- Toxicity and QoL questionnaires will be described using simple descriptive statistics.
- Assess the response rate of patients with advanced SGC treated with cabozantinib by using continuous tumor shrinkage end-points, as was advocated by Billingham et al¹¹ and Wason et al.¹²
- Tumor shrinkage will be shown in a waterfall plot.

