2. OBJECTIVES

Objectives will be analyzed separately in all 3 cohorts of c-MET positive, advanced SGC: (1) SDC, (2) ACC originated in the salivary glands or other sites of the body, (3) other SGC's

Primary Objective

- Assess the ORR. ORR is defined as the sum of the complete remissions plus partial responses.⁹ The best response will be used in each patient.

Secondary Objectives

- Assess the PFS. PFS will be defined as time from study enrollment until disease progression or death.
- Assess the OS. OS will be defined as time from study enrollment until date of death of any cause.
- Assess the DoR. DoR is defined as time from study enrollment until date of documented tumor progression or death
- Assess the toxicity of cabozantinib. Toxicity will be scored according to NCI CTC common criteria v 4.0.¹⁰
- Assess the QoL of patients treated with cabozantinib using EORTC questionnaires.
- Assess the response rate by using continuous tumor shrinkage end-points, as was advocated by Billingham et al¹¹ and Wason et al.¹²
- ctDNA will be assessed to evaluate whether response and disease progression can be predicted.

More details about the definitions and analysis of primary and secondary outcomes are described in chapter 8.1.

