4.2 Inclusion criteria

In order to be eligible to participate in this study, a patient must meet all of the following criteria:

- Disease specific
 - locally advanced, recurrent, and/or metastatic SGC (excluding sarcomas and mesenchymal tumors)
 - c-MET positive disease (see paragraph 4.1)
 - Measurable disease per RECIST version 1.1
 - Cohort-specific criteria
 - SDC cohort:
 - Direct inclusion (no objective tumor growth prior to inclusion needed)
 - ACC cohort:
 - Inclusion after objective growth in the last three months or complaints due to the disease
 - Other SGC's
 - Inclusion after objective growth in the last three months or complaints due to the disease
- General conditions
 - Age \geq 18 years
 - Eastern Cooperative Oncology Group performance status of 0 or 1.
 - Normal number of neutrophils and thrombocytes
 - Liver function:
 - ALT and AST $<$ 2.5 x upper limit of normal (ULN)
 - Total bilirubin \leq 1.5 x ULN (except for Gilbert's syndrome)
 - Serum albumin \geq 28 g/L
 - Renal function:
 - Creatinine $<$ 1.5 x ULN or calculated creatinine clearance \geq 40 ml/min
 - Urine protein/creatinine ratio \leq 113.1 mg/mmol (\leq 1 mg/mg) or 24-hour urine protein $<$ 1 g
 - Hemoglobin A1c (HbA1c) \leq 8% or a fasting serum glucose \leq 9 mmol/l

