8.2 Secondary study parameters/endpoints (if applicable)

- Assess the PFS
 - PFS is defined as time from study enrollment until disease progression or death.
 - Outcome will be scored as 'progressed' or 'censored' according to the FDA guidance for industry of clinical trial endpoints.⁹
- Assess the OS
 - OS is defined as time from study enrollment until date of death of any cause.
 - Analysis of OS will be done at the end of the study (study related follow-up will be until 3 years after start of treatment)
- Assess the DoR
 - DoR is defined as time from study enrollment until date of documented tumor progression or death
 - Only patients with a CR or PR will be included in the assessment of DoR.
- Assess the toxicity of cabozantinib in SGC patients
 - Toxicity will be scored according to NCI CTC common criteria v 4.0.
- Assess the QoL of SGC patients treated with cabozantinib
 - QoL will be assessed using the EORTC QLQ-C30, EORTC QLQ-H&N35, PSSHN and VAS questionnaires.
- Assess the response rate of patients with advanced SGC treated with cabozantinib by using continuous tumor shrinkage end-points, as was advocated by Billingham et al¹¹ and Wason et al.¹²
- ctDNA will be assessed to evaluate whether treatment response and disease progression can be predicted.

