8.2.1 Other study parameters (if applicable)

- History
 - Birth date
 - Gender
 - General medical history
 - Medication use
 - Allergies
 - SGC history: diagnosis date, location primary tumor, TNM stage at diagnosis, ex-PA?, AR-status, HER2-status, type of surgery, date of surgery, postoperative radiotherapy, date of radiotherapy, adjuvant systemic therapy, location of recurrence, date of recurrence, palliative treatments
- Clinical examination:
 - Vital signs
 - Body weight
- Laboratory tests: Hematology, biochemistry, urine (see assessments)
- ECG: QT time, abnormalities

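### ACC overall survival is counted from enrolment but compared with medians counted from recurrence (6.4 years) and metastasis (3.7 years), both longer than the 3-year follow-up

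*Combined protocol and SAP*

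**What the plan says.** Chapter 2 and section 8.2 start the survival clock at enrolment: "OS is defined as time from study enrollment until date of death of any cause". Section 8.2 also limits the observation period: "study related follow-up will be until 3 years after start of treatment".

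Section 10.2 gives two published figures with other starting points: "In ACC patients, median OS after disease recurrence is 6.4 years, and median OS after metastasis is 3.7 years". It then commits to the comparison: "OS of our study patients will be compared to these data and to OS data of phase II studies in ACC mentioned above". It names no test, alignment of time origins, landmark or caveat.

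The ACC entry rule in section 4.2 is "Inclusion after objective growth in the last three months or complaints due to the disease". Locally advanced, recurrent and metastatic disease are all eligible (sections 4.1 and 4.2). The history items in section 8.2.1 include "location of recurrence, date of recurrence, palliative treatments"; no separate date of metastasis is listed.

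**The concern.** Three clocks are in play: enrolment for the trial, and recurrence and metastasis for the two published medians. A patient who recurred some time ago and enters on recent growth or complaints has already survived the interval in between. That interval counts in the published figure but not in the trial's OS. A locally advanced patient with neither recurrence nor metastasis has no matching benchmark origin.

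In a single-arm trial, external figures are the only context for survival. If the curve looks worse or better than 3.7 or 6.4 years, a reader may credit or blame the drug for what the time origin produced.

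The second problem is the length of follow-up. If observation stops at 3 years, a trial median below 3 years can be seen, but one equal to or above either published median cannot. The comparison can then show shorter survival but not an equal or longer median.

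The point is confined to these two medians. The same sentence also names ACC phase II studies, but the documents do not give their time origins.

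**Working it through.** **The plan's own figure.** No design figure is stated for OS. The only one to reproduce is for response (sections 4.4 and 10.1): stop on 0 of 9, reject on more than 2 of 17. Summing P(X1 = x) × P(X2 ≥ 3 − x) over x ≥ 1, with 9 and then 8 patients, gives 0.0466 at a 5% response rate and 0.812 at 25%. The plan states 0.047 and 0.81, so it reproduces. OS does not enter this rule.

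**Inputs from the documents.** Published medians m = 3.7 and 6.4 years (10.2); follow-up 3 years (8.2); ACC cohort 9 or 17 patients (4.1).

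**Assumptions, because the documents give no values.** No drug effect; delay d from the benchmark event to enrolment of 0.5, 1 or 2 years; Weibull survival with shape k = 1.5 (rising hazard), 1 (constant) or 0.7 (falling).

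**Formulas.**
- Survival from the benchmark event: S(t) = 2^(−(t/m)^k).
- Median from enrolment, given survival to d: m × ((d/m)^k + 1)^(1/k) − d.
- Three-year survival from enrolment: S(d + 3)/S(d).
- Chance that 17 patients reach the median by 3 years: P(at least 9 deaths of 17), binomial, with everyone followed for 3 years.

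Example: m = 3.7, k = 1.5, d = 2. (2/3.7)^1.5 = 0.397; 1.397^(2/3) = 1.250; 3.7 × 1.250 − 2 = 2.62 years.

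**Results** (each cell: k = 1.5 / 1 / 0.7)

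| m (years) | d (years) | Median from enrolment (years) | 3-year survival | P(median reached), n = 17 |
|---|---|---|---|---|
| 3.7 | 0.5 | 3.3 / 3.7 / 4.6 | 0.55 / 0.57 / 0.61 | 0.35 / 0.28 / 0.18 |
| 3.7 | 1 | 3.0 / 3.7 / 5.0 | 0.51 / 0.57 / 0.64 | 0.48 / 0.28 / 0.13 |
| 3.7 | 2 | 2.6 / 3.7 / 5.6 | 0.44 / 0.57 / 0.67 | 0.68 / 0.28 / 0.08 |
| 6.4 | 0.5 | 6.0 / 6.4 / 7.5 | 0.77 / 0.72 / 0.71 | 0.01 / 0.02 / 0.03 |
| 6.4 | 1 | 5.7 / 6.4 / 8.0 | 0.74 / 0.72 / 0.73 | 0.02 / 0.02 / 0.02 |
| 6.4 | 2 | 5.1 / 6.4 / 8.8 | 0.70 / 0.72 / 0.76 | 0.04 / 0.02 / 0.01 |

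The shift from the time origin alone is:
- at a 2-year delay, −1.1 to +1.9 years (3.7-year median) and −1.3 to +2.4 years (6.4-year median);
- at 0.5 years, −0.4 to +0.9 and −0.4 to +1.1 years;
- zero with constant hazard or with no delay.

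**Follow-up.** 3 < 3.7 < 6.4. Under constant hazard, 57% or 72% of patients would be alive at 3 years, so 17 patients would give about 7.3 or 4.7 deaths. The median would be reached with probability 0.28 or 0.02. With 9 patients (at least 5 deaths needed) these become 0.33 and 0.07.

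**The case against.** The strongest case on the other side concerns weight.

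- **OS is secondary, with no test, threshold or decision attached.** This stands. The go/no-go is the response rule in section 10.1: "the null hypothesis will be rejected if more than 2 responses out of 17 patients are observed". That limits the harm to a misleading secondary conclusion.
- **The size rests on assumed delays and hazard shapes.** This also stands. Entry on recent growth is compatible with a fresh recurrence or metastasis, so the delay may be near zero. No direction can be claimed. But a bias of unknown size and sign is a reason not to make the comparison.
- **Sampling error is larger.** Under constant hazard with median 3.7 years and complete follow-up until the median is observed, 95% of sample medians from 17 patients lie between about 1.7 and 6.8 years, wider than any shifted 3.7-year median above. In 3-year survival, the delay moves the 3.7-year case by about −6 to +6 points at 0.5 years and −16 to +12 at 2 years, against a 95% half-width of about 24 points. This is correct, but imprecision adds to the mismatch and does not remove it. A confidence interval shows the imprecision; it does not show an error in the origin.
- **For 6.4 years there will seldom be a trial median to misread.** True, but the curve, or a statement that the median was not reached, would still be set against that figure.
- **Later survival data may be intended,** since section 10.4 calls an OS analysis at 3 years' median follow-up interim. The follow-up argument is therefore conditional on observation ending at 3 years, as section 8.2 says. The time-origin argument does not depend on it.

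**Conclusion.** The concern holds. By the protocol's own definitions, the planned ACC comparison sets survival from enrolment against medians from recurrence and from metastasis, with no alignment. The distortion could be nil, or it could exceed a year in either direction if the delay is about 2 years. Those sizes rest on the assumed delays, Weibull shapes and absence of a drug effect.

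That both medians lie beyond 3 years needs no model. In the delayed-entry scenarios, 17 patients would reach their median within 3 years with probability 0.08 to 0.68 if the 3.7-year figure applied, and at most 0.04 if the 6.4-year figure applied.

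This should be corrected because the analysis as written can mislead. It does not touch the primary conclusion on response.

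**What to change.** In section 10.2, replace the comparison with the two medians by wording such as:

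> For ACC, OS from enrolment will be reported as a Kaplan-Meier curve and as 3-year OS with a 95% CI (Greenwood variance, log-log transformation). The published medians from recurrence and from metastasis are given as background only and will not be compared with OS from enrolment. The comparison with OS data of the ACC phase II studies stays as planned.

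Optionally, and as exploratory only, OS could be counted from recurrence or metastasis with delayed entry at enrolment. Recurrence dates are already listed in section 8.2.1; a metastasis date would have to be added. This would not remove selection through growth or complaints at entry.

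**Cost.** The main change is wording only, with no extra visits or data. The downside is a wide interval. With no censoring before 3 years, 10 of 17 alive gives 33% to 78%, and 5 of 9 alive (cohort stopped after stage 1) gives 20% to 80%. As a rough check, 1.96 × √(0.57 × 0.43/n) is about 24 points for n = 17 and 32 points for n = 9.

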10.3 Other study parameters

Background variable will be described using simple descriptive statistics and will be presented in a table.

10.4 Interim analysis

- According to the Simon 2-stage design, interim analysis of treatment efficacy will be done after 9 patients in each cohort. Treatment efficacy will be established by the response rate, in which a treatment response is defined as a complete remission or partial response, based on RECIST version 1.1 criteria. In case of 0 response, this

cohort will be terminated. In case of ≥ 1 response(s), 8 additional patients will be included in stage 2. This interim analysis will be performed by the researcher. The monitor will check the responses, in order to establish whether patients can be included in stage 2.

- For OS, a planned interim analysis will be done after a median follow-up of 3 years. The monitor will analyze interim safety and efficacy data in according to the NFU guideline 'Kwaliteitsborging mensgebonden onderzoek 2.0', for moderate risk studies. Next to this, the monitor will check if the study can proceed to stage 2, based on treatment efficacy in stage 1, as described at the first bullet of this paragraph.

11. ETHICAL CONSIDERATIONS

11.1 Regulation statement

The study will be conducted according to the principles of the Declaration of Helsinki (version 8, 19 October 2013), in accordance with the Medical Research Involving Human Subjects Act (WMO), the personal data protection act (Wet Bescherming Persoonsgegevens), and the Medical Treatment Agreement Act (WGBO).

11.2 Recruitment and consent

Patients will be informed about the study by their treating physician during normal patient care. Detailed information about the study can be offered by the investigators during normal patient care or by phone call. If a patient decides to participate, the baseline study visit will be planned, which starts with reviewing inclusion and exclusion criteria and signing the IC.

11.3 Objection by minors or incapacitated subjects (if applicable)

Not applicable

11.4 Benefits and risks assessment, group relatedness

Benefits: because cabometyx has not been tested in SGC patients before, the chance of responding to treatment is unknown. The Simon 2-stage design will be used in order to prevent exposure of too many patients to ineffective treatment without discarding a potential effective treatment because of treatment failure in some patients.

Risk assessment: Safety of Cabometyx is well known because of studies in renal cell carcinoma.³ The most common serious adverse reactions associated with cabozantinib are abdominal pain (3%), pleural effusion (3%), diarrhoea (2%), and nausea (2%). The most frequent adverse reactions of any grade (experienced by at least 25% of patients) included diarrhoea (74%), fatigue (56%), nausea (50%), decreased appetite (46%), palmar-plantar erythrodysesthesia syndrome (PPES) (42%), hypertension (37%), vomiting (32%), weight decreased (31%), and constipation (25%).²⁶

Group relatedness: the study does not involve minors and/or incapacitated subjects

